CASE
COMPREHENSIVE
CANCER CENTER

STUDY NUMBER: CASE 4623

ClinicalTrials.gov NCT #:

Protocol Date: 5/16/2023

STUDY TITLE: Short contact protocols to reduce pain during treatment of actinic keratoses with 10% ALA gel red-light photodynamic therapy (PDT)

PRINCIPAL INVESTIGATOR: [name]. Ph.D.
Desk A61, Department of Dermatology
Dermatology and Plastic Surgery Institute
Cleveland Clinic
[name]
[name]
[REDACTED]

STATISTICIAN: [name].
Department of Quantitative Health Sciences
Cleveland Clinic Foundation
[name]
[name]

STUDY COORDINATOR: [name]
Department of Dermatology, A61
Cleveland Clinic Foundation
[name]
[name]
[REDACTED]

SPONSOR: Investigator-initiated study
[name] M.D. Ph.D.

SUPPORT/FUNDING: Biofrontera, Inc.
[name]

[name]

SUPPLIED AGENTS AND DEVICES:

- (1) Ameluz gel, 10% aminolevulinic acid, an FDA-approved drug;
- (2) BF-RhodoLED®, an FDA-approved light source

Title: Short contact protocols to reduce pain during treatment of actinic keratoses with 10% ALA gel-red light photodynamic therapy (PDT)

Principal Investigator: [name]. Ph.D.

PRINCIPAL INVESTIGATOR SIGNATURE:

Date: _____

SUMMARY OF CHANGES

Protocol Date	Section	Change
		Initial IRB approval

STUDY SCHEMA

Timeline of procedures for patients enrolled in the study.

	VISIT 1 PDT treatment session #1	VISIT 2 Photos of skin redness	VISIT 3 PDT treatment session #2	VISIT 4 Final lesion counts
Scheduled visit: → Procedure: ↓	Day 1	Day 3 ±1 day	Week 8 ±1week	Month 3-6
Sign informed consent	X			
Examine patient, mark each lesion with a pen, and count the lesions	X		X	X
Take photographs in professional studio (frontal view and side views) to document inflammation.	X	X		
Take photographs using clinic iPhone camera to document lesion counts (pen-marks)	X		X	X
Apply topical ALA gel and incubate for 10, 20, or 60 min prior to turning on the light source (as per assigned study arms A, B, or C, respectively)	X		X	
Illuminate with red light for 20, 10, or 10 min (as per assigned study arms A, B, or C, respectively)	X		X	
Record patient-reported pain level (VAS)	X		X	
Give the patient a questionnaire to fill out at home (to describe side-effects on each of the 6 days post-PDT)	X		X	
Provide patient with a hat, sunscreen and aftercare instructions	X		X	
Patient satisfaction survey				X

PROTOCOL SUMMARY

Protocol Number/Title	Short contact protocols to reduce pain during treatment of actinic keratoses with 10% ALA gel red-light photodynamic therapy (PDT)
Study Phase	Investigator-initiated study
Brief Background/Rationale	Ameluz 10% ALA gel is a topical FDA-approved photosensitizer that is used in combination with red light (BF-RhodoLED® unit, an FDA-approved device) to treat actinic keratoses. Red light illumination is typically administered after a 3-hour incubation with the ALA gel, and is associated with an undesirable side effect, stinging pain. The proposed clinical study will test the hypothesis that one or more shorter incubation regimens can provide excellent treatment efficacy while reducing or eliminating the pain that is typically experienced by patients with the conventional 3-hour regimen.
Primary Objective	Primary Endpoint(s) Efficacy Pain
Secondary Objective(s)	Secondary Endpoint(s) Patient satisfaction. AE profile/Safety
Exploratory Objective(s)	
Correlative Objective(s)	None
Sample Size	30 participants
Disease sites/Conditions	Actinic Keratosis
Interventions	Standard PDT using topical aminolevulinate (10% ALA gel) followed by red light (FDA-approved protocol) for actinic keratosis.

ABBREVIATIONS

CCCC	Case Comprehensive Cancer Center
CRF	Case Report Form
CRU	Clinical Research Unit
DSTC	Data Safety and Toxicity Committee
FDA	Food and Drug Administration
ICF	Informed Consent Form
IRB	Institutional Review Board
PRMC	Protocol Review and Monitoring Committee
SOC	Standard of Care
CCF	Cleveland Clinic Foundation
UH	University Hospitals
AK	Actinic Keratosis
ALA	Aminolevulinic acid
PpIX	Protoporphyrin IX

TABLE OF CONTENTS

1.0 Specifications for Ameluz

2.0 Specifications for the BF-RhodoLED®red light source

3.0 Post-PDT Side Effects Journal

4.0 Patient Satisfaction Questionnaire

1.0 Introduction

1.1 Background and Significance

Actinic keratoses (AK), are dysplastic precancerous lesions of the skin with potential to develop into squamous cell carcinoma. AKs are extremely common and are typically observed in sun-damaged skin of Caucasian individuals. It is important to treat AKs because of the possibility that 2-5% of them may evolve into squamous cell carcinoma (SCC). Progression of AK to SCC is even higher in immunosuppressed patients, e.g. organ transplantation recipients. Amongst currently available treatments for widespread AK that include surgical (cryotherapy, scalpel excision) and medicinal approaches (topical 5-fluorouracil, imiquimod, diclofenac cream) approaches, a relatively new modality called photodynamic therapy (PDT) has several distinct advantages [1]. PDT is a method in which a topical drug such as aminolevulinic acid (ALA) or methyl-ALA is applied to AK lesions, where it is taken up selectively by precancer cells [2]. Within the cells, ALA is converted into a photosensitizer (protoporphyrin IX, PpIX) within mitochondria, whereupon a strong visible light is used to activate the PpIX, triggering photochemical reactions such as the generation of reactive oxygen species that kill the precancer cells. PDT excels as a modality to treat widespread areas of field cancerization, and it has the additional advantages of minimal down time and rapid recovery, lack of scarring, lack of pigmentary changes, and repeatability [3]. However, a limiting factor with all current versions of aminolevulinate-based PDT is *stinging pain* that patients often have to endure during illumination [4]. This pain is proportional to the amount of the target photosensitizer (PpIX) that is present in the skin prior to the start of illumination. Pain is a frequent occurrence in patients who receive PDT with standard protocols currently approved by the FDA, all of which required an ALA incubation period of many hours, i.e., 14-18 hr with Levulan Kerastick (20% ALA), 3 hr with Metvixia (16% methyl-ALA), and 3 hr for Ameluz (10% ALA nanoemulsion). Metvixia and Ameluz, also require that an occlusive dressing be applied to enhance penetration. Metvixia is no longer available in the US, leaving Ameluz and Levulan as the only two viable options for dermatologists providing PDT in the United States. Ameluz has generated significant interest due its properties as lipid-based nanoemulsion that exhibits superior uptake into AK lesions [5].

To date, the problem of PDT treatment-associated pain has become a serious impediment to the full implementation and acceptance of PDT by the general population of dermatology patients. Stories about painful experiences during PDT are shared online or by word of mouth, and tend to generate fear and reluctance to undergo PDT. Another issue is lack of convenience. Traditional PDT can require many hours of waiting time in the office, which tends to discourage patients and physicians from embracing PDT as enthusiastically as they should, given its potential benefits. A third issue is the requirement for occlusion when using Ameluz and red light. While the latter protocol was originally designed to achieve maximal AK clearance for a small number of AK in a defined area, it is not ideal for broad field treatment of AK above the neck, particularly on the face where occlusive dressings are very inconvenient.

1.2 Scientific rationale for the proposed study

The proposed pilot study will simultaneously address the 3 current drawbacks of PDT using Ameluz and red light, which are: (1) pain during illumination, (2) lengthy incubation periods, and (3) the inconvenience of plastic wrap occlusion.

The rationale for this study is based upon recent findings and observations from another version of PDT technology for actinic keratosis, namely, 5-ALA (Levulan) and blue light, in which a short-incubation regimen was developed and shown to provide excellent efficacy while generating minimal pain during illumination [6, 7]. The principle exploited by those studies is that conversion of ALA to PpIX begins as soon as ALA is applied to the lesions [8]. Thus PpIX can be photoactivated, even at low levels, by illumination with blue or red light, thereby destroying mitochondria and triggering a somewhat delayed yet highly effective inflammatory-immunological response to eliminate the lesions [9]. Previously, in developing a ‘painless blue light protocol’, our group compared two Levulan/blue light protocols in a bilateral comparative format (each patient serving as his/her own control). On one side, AK lesions were treated using the shortest drug incubation time that was known to produce significant lesion clearance (1 h ALA incubation), followed by illumination for 16 min 40 sec (as in the standard FDA-approved blue light protocol). This produced a pain level, on average, ~5 on a 1-10 visual-analog scale. On the contralateral side of the face, AK lesions were treated with immediate (simultaneous) illumination, in which 20% ALA solution was applied and then blue light was shone for either 30 min, 45 min, or 60 min. In all three of these timed cohorts, patients reported very low pain levels (~1 out of 10), and yet they developed erythema and lesion clearance rates at 3 month that were similar (statistically non-inferior) to the ‘traditional’ 1 hr ALA incubation period [7]. This study demonstrated that good treatment efficacy can still be obtained even when pain is minimized using an ALA short-contact approach.

In the current study, we will seek to translate the findings observed with 5-ALA/blue light (above), into a regimen with 10% ALA gel and red light, and assess its feasibility.

1.3. Rationale for the experimental design.

The experimental strategy is to examine short-contact Ameluz/red light protocols in a well-established PDT clinic, to explore pain reduction and treatment efficacy using an FDA-approved PDT drug (Ameluz) and light source (BF-RhodoLED® red light panel) under conditions that have been modified to be sub-maximal (i.e., using shorter than usual drug-incubation times). Our hypothesis is that patient comfort will be greatly improved, yet an acceptable treatment efficacy will be maintained. We plan to invite patients who are already scheduled to undergo PDT treatment in [name] clinic for actinic keratoses of the face to participate in the study.

The following scientific questions will be asked and addressed in a manner consistent with scientific principles as well as practical considerations.

- (1) Will the application of the nanoemulsion (10% ALA gel), in the absence of occlusion, still achieve significant inflammation and lesion clearance?
- (2) Will shortened incubation times of Ameluz still achieve significant inflammation and lesion clearance?
- (3) Will the new test regimens achieve reduced pain during illumination?
- (4) Will the new test regimens be safe?

Consideration and discussion about the rationale for how we developed the proposed short-contact protocols, in relation to each scientific question, is provided below:

(1) Will the nanoemulsion (ALA gel) still work in the absence of occlusion?

Answer: Because the 10% ALA gel has much better penetration than 5-ALA/Kerastick that was shown to work without occlusion, it seems highly likely that 10% ALA gel will penetrate lesions and accumulate sufficient PpIX even in the absence of occlusion.

(2) Will short 10% ALA gel incubation times still achieve significant inflammation and lesion clearance?

Answer: For comparing the efficacy of 10% ALA-gel-red light treatment, the benchmark is the 3-hr incubation regimen approved by the FDA, which uses 10% ALA gel (under occlusion), followed by 8 min (37 J/cm²) of red light [10, 11]. However, we can also point to a study by Nestor et al. that compared Ameluz and Levulan directly, and showed equivalent AK lesion clearance when each agent was applied for 1 hour (without occlusion) followed by a standard 1000 sec exposure to blue light [12]. Those results indicate that short 10% ALA gel incubation times without occlusion can still achieve significant inflammation and lesion clearance. To develop this idea further for 10% ALA gel and red light, we have extrapolated from another study using blue light PDT, our clinical trial [7] in which the duration of blue light illumination was drastically shortened but yet achieved surprising efficacy. That work involved several different study arms. In one arm, the original 14-18 hr 20% ALA solution incubation, was shortened to 1 hr ALA incubation followed by a standard 16 min 40 sec blue light illumination. Based upon those results, we believe that the Ameluz incubation time can be reduced from 3 hr to 1 hr, followed by a standard 10 min (37 J/cm²) of red light to achieve a reasonable therapeutic effect. In a different study arm from Kaw et al, the 20% ALA solution incubation time was shortened to zero, i.e., ALA was applied and then blue light was turned on for 30 minutes to provide a simultaneous incubation/illumination. Pain was minimized, yet the amount of AK lesion clearance achieved by the simultaneous regimen was remarkably similar (statistically non-inferior) to AK clearance seen after the 1-hour ALA incubation regimen. For the red light protocol proposed here, we will choose a total Ameluz incubation time of 30 min, and perform simultaneous incubation/illumination using two slight variations. In **Regimen A**, there will be a 10 min ALA incubation time followed by 20 min (75 J/cm²) of red light. **Regimen B** will have a 20 min incubation time followed by 10 min (37 J/cm²) of red light. As a third arm (control), **Regimen C** will have a 1 hr incubation followed by 10 min (37 J/cm²) of red light, which is comparable to the arm of the Kaw study that used 1 hr incubation followed by ~16 min (10 J/cm²) of blue light. By modeling our test conditions after Kaw et al [7], we expect to observe outcomes similar to that study (i.e., equivalent inflammation, equivalent AK lesion clearance rates, and reduced pain). The biological rationale for simultaneous ALA incubation/illumination is that PpIX is continuously produced and consumed, thereby producing therapeutic effects over a wide range and with a wide safety margin.

(3) Will the new test regimen achieve reduced pain during illumination?

Answer: The likelihood is extremely high that the test regimen (or at least regimens A and B) will be nearly painless. There is now substantial evidence in the literature, showing that if visible light is delivered continuously while PpIX levels are low, then PpIX does not build up to high enough levels within pre-cancer cells to trigger pain. Instead, the PpIX is activated and destroyed as soon as it is produced. Without high PpIX concentrations in pre-cancer cells, there is no PpIX

concentration gradient and therefore no PpIX leakage from epithelial pre-cancer cells into neighboring nerve endings. The latter is the main cause of pain during traditional PDT [13].

(4) Will the new test regimen be safe?

Answer: Yes, because all test conditions (drug concentration, drug incubation time, illumination time) are either at or below the FDA-approved levels for Ameluz paired with the BF-RhodoLED® red light source.

The possible benefit of this study will be the demonstration of suggestive evidence for a new ALA-PDT regimen using Ameluz/red light for actinic keratosis, that provides a therapeutic result equivalent to current regimens, yet minimizes the pain that patients must endure.

2.0 OBJECTIVES

2.1 Primary Objective

- To demonstrate that a short-contact PDT protocol with Ameluz and red light generates less pain during illumination than the standard FDA-approved protocol currently used.
- To test the hypothesis that a short-contact PDT protocol with Ameluz and red light will produce lesion clearance outcomes that are statistically non-inferior to the traditional, painful protocol.

2.2 Secondary Objective(s)

- To test the hypothesis that a short-contact PDT protocol with Ameluz and red light will generate an inflammatory response.
- To test the hypothesis that a short-contact PDT protocol with Ameluz and red light will be better tolerated and provide higher patient satisfaction than the currently practiced protocol.

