3.0 STUDY DESIGN

3.1 Study protocol description

The objective of this study is to test three new PDT regimens for actinic keratoses (AK) of the face that promise to greatly reduce the pain normally associated with the procedure. The new regimens, called A, B, and C, respectively, will use a photosensitizer (aminolevulinic acid, 10% ALA gel, Ameluz®) and an activating red light illumination source (BF-RhodoLED® red light panel, 635 nm) from Biofrontera, Inc. Both ALA gel and the 635 nm light source from Biofrontera are currently FDA-approved for broad-area PDT treatment of AK. The approved FDA treatment (standard regimen) specifies that ALA gel be applied topically and left on for 3 hours, followed by exposure to red light for 10 minutes. Here, the timing for topical ALA gel incubation will be shortened, to test the hypothesis that pain experienced during red light illumination can be significantly reduced while still preserving the efficacy of the procedure in terms of lesion clearance (pain and efficacy are primary endpoints). Safety and patient satisfaction will also be assessed (secondary endpoints). Timing for the 3 regimens will be as follows: **A**, ALA gel for 10 min, then red light for 20 min while ALA gel is left incubating. **B**, ALA gel for 20 min, then red light for 10 min while ALA gel is left incubating. **C**, ALA gel for 60 min, then red light for 10 min. We hypothesize that each of the new regimens will cause significantly less pain than the

current standard regimen for ALA gel/red light PDT, and that a lesion clearance response will be achieved that is similar (i.e., statistically non-inferior) to the standard treatment regimen.

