4.0 PATIENT SELECTION

4.1 Inclusion Criteria

Males or females, must be at least 18 years of age, with a minimum of 10 actinic keratoses lesions on the face. A total of 10 subjects will be enrolled for each of the study arms A, B, and C. The study will be conducted at the Cleveland Clinic.

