5.0 REGISTRATION

5.1 Recruitment

This study will be introduced to patients who meet eligibility criteria during their routine PDT visits and will either be provided a copy of the consent form to take home and review or give permission to be contacted for more information regarding the study. If the study coordinator is available, they will briefly meet with the patient to provide copy of informed consent form and explain study design, and the patient will be instructed to review consent form and call study coordinator with any questions and/or if they would like to move forward with participation. If the study coordinator is not available to meet with the patient during their routine visit, they will be notified and will call the patient to explain the study, and will also send a copy of the consent form via mail or email to the patient to review. If the study is not introduced to the patient, but they are eligible, the study coordinator can send a copy of our recruitment letter to patient via mail or MyChart to be followed up by a phone call. Recruitment will also be aided by IRB-approved advertisements posted in the Dermatology waiting room or other approved locations.

5.2 Consent:

Once the patient reviews the copy of the consent form that was provided by the study coordinator, either in person or via mail or email and the patient expresses interest in participating he/she will be scheduled for the first study visit. Once the patient arrives in clinic, the study will be explained once again, along with the chance to ask additional questions, and if the patient indicates continuing willingness then he/she will sign the consent form and be considered enrolled.

5.3 Randomization:

Upon enrollment, each patient will be assigned to one of the three treatment regimens (A, B, or C) using a block-randomization scheme that will be generated by staff in the Research Pharmacy (Investigational Drug Service) of the Cleveland Clinic; this assignment will insure an equal distribution of study patients across the 3 groups.

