11.0 STUDY PARAMETERS AND DETAILED STUDY CALENDAR

Details of 10% ALA application and red light treatment were described in detail under Section 6.0, “Treatment Plan”. The timing of visits is summarized below and in section 11.5 (“Calendar”).

11.1 **PDT treatment (Visit 1)**

All AK lesions are measured clinically and photographed. The clinician applies 10% ALA gel to entire face, without occlusion, and allows it to incubate if for either 10 min, 20 min, or 60 min, depending upon the study arm assignment. The patient will then be exposed to red light (BF-RhodoLED® device) for either 10 min or 20 min, as per the assigned study arm.

11.2 **Post-treatment assessment of side-effects (Visit 2)**

The patient will return at day 3 (± 1 day) for facial photographs to document their erythema reaction. They will also be asked about their side-effects, and insure that they know to fill out the side-effects questionnaire during the 6 days post-PDT.

11.3 **PDT treatment (Visit 3)**

This will occur 8 weeks (± 1 week) after Visit 1. All AK lesions will be measured clinically and photographed and if any remain, then the same PDT treatment regimen used at Visit 1 will be employed again here for a second round of treatment.

11.4 **Final observation (Visit 4)**

This will occur 3-6 months after Visit 1. The subject will return for final skin exam, lesion counts, and photography. A patient satisfaction questionnaire will also be administered at this visit. The large scheduling visit window is designed to maximize the likelihood of patient compliance, since many patients with AK are retirees who spend many months traveling and spend their winters in warmer climates far from Cleveland.

11.5 **Study Calendar**

CALENDAR. Timeline of procedures for patients enrolled in the study.

	VISIT 1 PDT treatment session #1	VISIT 2 Photos of skin redness	VISIT 3 PDT treatment session #2	VISIT 4 Final lesion counts
Scheduled visit: → Procedure: ↓	Day 1	Day 3 ± 1 day	Week 8 ± 1 week	Month 3-6
Sign informed consent	X			
Examine patient, mark each lesion with a pen, and count the lesions	X		X	X
Take photographs in our professional studio (frontal view and side views) to document inflammation.	X	X		
Take photographs using clinic iPhone camera to document lesion counts (pen-marks)	X		X	X

Apply topical ALA gel and incubate for 10, 20, or 60 min prior to turning on the light source (as per assigned study arms A, B, or C, respectively)	X		X	

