12.0 MEASUREMENT OF EFFECT

Endpoints to be evaluated are as follows: Pain reported by the patients during illumination will be measured on a subjective 11-point visual-analog scale (VAS). Treatment response will be evaluated by clinical exam and follow-up photographs at the two follow-up visits.

Endpoints will be:

- 12.1 Pain during illumination (VAS scale 0-10) at 1 min, 5 min, and 10 min
- 12.2 100% lesion clearance rates
- 12.3 75% lesion clearance rates
- 12.4 Visual differences observed in the before-and-after photos
- 12.5 Subject satisfaction questionnaire
- 12.6 Adverse Events- Patients' side effects log (6 days post-PDT) and Investigator assessment.

Regarding lesions clearance rates (items 12.2 and 12.3), the final efficacy outcome will be defined as the lesion counts after two treatments, and these final counts are what the estimated enrolled sample sizes are based on. Lesion status after 1 PDT treatment will also be analyzed, but not considered in the analyses of noninferiority.

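### Higher satisfaction than the 3-hour regimen cannot be tested, because no patient receives that regimen and no reference is cited; for tolerability, only pain has a specified comparator

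*Combined protocol and SAP*

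**What the plan says.** Section 2.2 states a comparative hypothesis: short-contact treatment "will be better tolerated and provide higher patient satisfaction than the currently practiced protocol". Section 3.1 describes the approved standard, which "specifies that ALA gel be applied topically and left on for 3 hours, followed by exposure to red light for 10 minutes".

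The same section says the study will "test three new PDT regimens for actinic keratoses (AK) of the face". These are A (10 min gel, 20 min light), B (20 + 10) and C (60 + 10). Under Section 5.3, "each patient will be assigned to one of the three treatment regimens (A, B, or C) using a block-randomization scheme", and Section 4.1 adds: "A total of 10 subjects will be enrolled for each of the study arms A, B, and C".

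Satisfaction is measured once. Section 11.4, on Visit 4, says: "A patient satisfaction questionnaire will also be administered at this visit". Section 12.0 lists it only as "Subject satisfaction questionnaire", without a score, a contrast or a reference value. Side effects are recorded in a 6-day log after each treatment session. The Protocol Summary and Section 3.1 make satisfaction and safety secondary endpoints, and pain and clearance primary.

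**The concern.** The hypothesis names the 3-hour regimen as comparator, and nobody in the trial receives it. For the two primary endpoints the plan fills this gap with published 3-hour results. For satisfaction it supplies nothing, and for the side-effect journal it specifies nothing. Followed as written, the plan produces satisfaction scores with no counterpart, and a report of higher satisfaction than current practice would have no support. Meanwhile the randomised contrasts that the data can inform, A versus C and B versus C, are not named for these endpoints.

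**Working it through.** **1. What each outcome can be compared with.**

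| Outcome | Patients on 3-hour regimen | Published 3-hour value in the plan | Comparison described |
|---|---|---|---|
| Pain (primary) | 0 | 5.5 (95% CI 4.7–6.2) first session; 5.8 (4.7–6.9) second | Yes, historical, Section 14.2 |
| Clearance (primary) | 0 | 78 ± 15%, n = 31 | Yes, Section 14.2 |
| Satisfaction (secondary) | 0 | None | None |
| Side-effect journal (secondary) | 0 | None specified | None |

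With no patients on the comparator and no reference mean, proportion or SD, no test of satisfaction against the 3-hour regimen can be formed.

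**2. Whether regimen C can stand in for current practice.** Section 1.3 calls C a control. Section 3.1 counts it among the new regimens, and Section 14.2 sets the 1-hour regimen as the experimental group against 3-hour data. A or B versus C is therefore a comparison among short regimens.

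**3. The plan's own sample-size figure.** Section 14.2 states 80% power with 10 per group, for non-inferiority of clearance (margin 25, true difference 10, SD 13). The formula n = 2·SD²·(z₁ + z₂)²/(margin − difference)² gives 2·169·(1.645 + 0.842)²/15² = 9.3, so 10, at one-sided 0.05. With z₁ = 1.96, which matches the stated two-sided 0.05, it gives 11.8, so 12. Either way the figure concerns clearance and says nothing about satisfaction.

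**4. What 10 versus 10 can show on satisfaction.** This assumes a roughly continuous score with a common SD; the scale was not seen.

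- Detectable difference, 80% power, two-sided 5%: (1.96 + 0.84)·√(2/10) = 1.25 SD by normal approximation, and 1.32 SD with the t distribution on 18 degrees of freedom.
- Power for a true difference of 0.8 SD (t): about 40%.
- Half-width of a 95% interval: 2.10·√(2/10) = 0.94 SD.
- These figures make no allowance for two contrasts. At two-sided 2.5% each, the detectable difference rises to about 1.48 SD (t).

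These numbers describe the substitute contrast. They do not measure the defect in Section 2.2, which is the missing comparator.

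**The case against.** A reader might infer that the whole of this objective is untestable, tolerability included. The documents do not support that. Pain is the main tolerability problem in Sections 1.1 and 1.2, and Section 14.2 commits to comparing it with published 3-hour results. If tolerability includes pain, a historical comparator exists. It remains a cross-study comparison and belongs to a primary endpoint.

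It would also be too strong to say that nothing exists to set beside the side-effect journal. Section 8.1.2 lists reaction rates (stinging or burning over 50%, erythema 35%, oedema over 35%), and reference 5, the source for pain, is by its title a study of safety as well as efficacy. But the listed rates are rough, are not tied to the 3-hour regimen and are not named as a comparator, and what reference 5 reports on side effects cannot be seen here. What stands is that no comparator is specified.

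Appendices 3 and 4 (journal and questionnaire) are listed in the contents, but their text was not available. Sections 1.3 and 5.1 recruit patients already scheduled for or attending routine PDT, so some may have had it before, and the questionnaire might ask them to compare. This cannot be ruled out. Such answers would be uncontrolled recall, and no analysis of them is described.

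Finally, this is a secondary objective in a 30-patient pilot, and no sample size rests on it. That limits the consequence, but it also favours an estimation objective over a promised hypothesis test.

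**Conclusion.** The concern holds for satisfaction: superiority over the 3-hour regimen cannot be tested with the data and references in the supplied text. For tolerability it holds in part: pain has a specified historical comparator, and the 6-day journal has none. It does not extend to saying that tolerability as a whole cannot be compared, or that no within-patient information on earlier PDT could exist.

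The randomised contrasts A versus C and B versus C are available but imprecise: about 1.3 SD for 80% power and an interval of about ± 0.94 SD, assuming a continuous score and 10 evaluable patients per arm. No blinding is described, and patients will notice whether they wait 10, 20 or 60 minutes, so self-reported satisfaction is open to expectation. Neither contrast involves current practice.

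**What to change.** Split the objective in Section 2.2 and add a matching sentence to Section 14.

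- **Tolerability against the 3-hour regimen:** limit this to pain, place it under the primary endpoint, and label it a historical comparison with the published values already in Section 14.2.
- **Satisfaction and side effects:** drop the reference to current practice. Suggested wording: *To estimate, with 95% confidence intervals, the difference in satisfaction at Visit 4 and in side effects from the 6-day journal between A and C and between B and C.*
- **Limits to state:** no blinding is described, and 10 per arm gives 80% power only for about 1.3 SD on a continuous score. Any patient recall of earlier PDT is descriptive only.

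If the sponsor wants to keep the comparison of satisfaction or side effects with current practice, it needs a cited 3-hour reference for each outcome with a stated analysis, or concurrent patients on that regimen.

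The recommended change is wording only, with no extra patients, visits or forms. The downside is a more modest claim.
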